6.4.3 Handling Dropouts or Missing Data

6.4.3.1 Imputation of Missing Efficacy Data

The missing data handling rule for the study eye will be applied for the efficacy endpoints.

Missing data from subjects who discontinue the study before POD15 assessments without taking rescue medication:

For subjects who prematurely discontinue the study without taking rescue medication, the LOCF approach will be used to impute the missing data. The last observation will be the last assessment value after the first dose of study drug and up to two days following the last dose of study drug.

Missing data from subjects who discontinue the study and take rescue medication before POD15 assessments:

For both categorical and continuous secondary efficacy endpoints of ACC grade, ocular pain grade and ACF grade, subjects who take rescue medication before POD15 assessments and prematurely discontinue the study, the LOCF approach will be used to impute the missing data. The last observation will be the last assessment value after the first dose of study drug and prior to starting rescue medication.

Intermittent missing data:

The likelihood of having intermittent missing data is low. For subjects with intermittent missing data for efficacy endpoints, the LOCF approach will be applied to impute the missing data, i.e., using the data collected from the most recent prior visit after the first dose of study drug.

If no data can be carried forward (i.e., missing assessments at POD 4 visit or no available post-baseline assessments), missing data will be treated as missing for the continuous endpoints and will be considered as 'Non-responder' for the categorical endpoints.

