6.3 Subject Early Termination (Withdrawal)

Any subject who wishes to voluntarily discontinue study drug or withdraw from participation in the study for any reason is entitled to do so without obligation. If a subject requests to discontinue the study drug, the subject will be withdrawn from the study as an Early Termination (see [Section 6.2.7](#)).

The Investigator may discontinue any subject from study drug or from study participation, if deemed necessary at any time during the study for any reason including, but not limited to:

- The investigator considers that the subject requires alternative medication that is incompatible with further continuation of the study drug or participation in the study.
- Occurrence of any medical condition or circumstance that exposes the subject to substantial risk and/or does not allow the subject to adhere to the requirements of the protocol.
- Any SAE, clinically significant AE, severe laboratory abnormality, intercurrent illness, or other medical condition that indicates to the Investigator that continued participation in the study is not in the best interest of the subject or that continued participation could affect study objectives.
- Any woman who reports becoming pregnant while participating in the study. Information on the pregnancy and outcome will be requested by the Investigator.
- Subject's continued failure to comply with protocol requirements or study-related procedures after being instructed on the correct requirements or procedures by the Investigator or site personnel.
- Termination of the study by the Sponsor, FDA, or other regulatory authority.

In the event that early termination/withdrawal of a randomized subject is necessary ('withdrawn' subject), the Investigator should make every attempt to complete the Visit 6 assessments and perform a urine pregnancy test as soon as possible ([Table 1](#)). Note: the Visit 6 ocular assessments need to be performed on both eyes.

The reason for early termination/withdrawal of a subject should be recorded in the source documents and entered in the eCRF.

Subjects who are terminated early from the study will not be replaced.

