9.4 Rescue Management

9.4.1 Criteria for Starting Rescue Medication

Any subject not responding to the study drug because of lack of efficacy at any time after randomization at Visit 2 (POD1) may be rescued and placed on an appropriate alternative therapy determined by the Investigator.

In general, at any visit, a subject with worsening inflammation or showing no improvement in degree of inflammation compared with the previous visit is eligible for rescue therapy at the discretion of the Investigator. However, the following guidance is provided to Investigators for consistency in the way subjects are rescued:

1. Subjects who, on examination of the anterior chamber, have one or more of the following quantitative criteria should be rescued and discontinued from study drug dosing and placed on rescue mediation:
 - An increase of ACC count by > 15 cells from the Visit 2 (POD1) pre-dose baseline.
 - A ≥ 2 grade increase in ACF grade from the Visit 2 (POD1) pre-dose baseline.

2. Subjects who have the following qualitative criteria may be rescued. If the subject is rescued, the study drug should be discontinued and rescue medication started:

- Subjects who have pain and/or photophobia that does not improve, even when there is an improvement in ACC count and/or ACF grade, may be rescued at the discretion of the investigator.
- Subjects who have pain and/or photophobia that worsens may be rescued at the discretion of the investigator.

Initiation of rescue medication is at the discretion of the Investigator. However, it is recommended that the Investigator uses the above guidance to determine when to rescue a subject. If the quantitative ACC count or ACF grade criteria are not met, the Investigator should discuss the qualitative reason(s) for rescue with the Study Medical Monitor for consistency across the study.

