10.3.2 Analysis of Efficacy

All efficacy analyses and summaries will be based on assessments in the study eye for each subject.

Subjects who are rescued at any time prior to Visit 5 (POD15) will be considered as treatment failures for the primary efficacy endpoints and the relevant secondary efficacy endpoints. For subjects who discontinue from the study prior to Visit 5 (POD15), the last observation carried forward (LOCF) approach will be used to impute missing data.

For continuous secondary efficacy endpoints, the LOCF approach will also be used to impute the data at visits after subjects are rescued.

The ACC count will be graded as shown below:

Grade	0	1	2	3	4
ACC Count	0 cell	1-5 cells	6-15 cells	16-30 cells	> 30 cells

10.3.2.1 Analyses of Primary Efficacy Endpoints:

The primary efficacy analyses to compare APP13007 against placebo will be conducted on the ITT population using the Pearson Chi-square statistic. Fixed sequence testing will be employed to maintain the 2-sided alpha = 0.05. The primary analyses will first test the difference between treatments in the proportion of subjects with ACC count = 0 (Grade = 0) at POD8 (Visit 4) maintained through POD15 (Visit 5). If the test is statistically significant at the 2-sided alpha = 0.05 level in favor of APP13007, the difference between treatments in the proportion of subjects with Ocular Pain grade = 0 at POD4 (Visit 3) maintained through POD15 (Visit 5) will be tested at the two-sided alpha = 0.05 level.

To confirm the robustness of primary analysis results, sensitivity analyses, including using observed data from all subjects, will be performed. The detailed sensitivity analyses will be described in the SAP.

10.3.2.2 Analyses of Secondary Efficacy Endpoints:

Mean change-from-baseline in ACC Grade, ocular Pain Grade, ACF Grade and visual acuity at PODs 4, 8 and 15 will be analyzed using an analysis of covariance (ANCOVA). The ANCOVA model will include treatment as a fixed effect and baseline as a covariate. The rest of secondary efficacy endpoints will be analyzed using the same method described for the primary efficacy endpoints.

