6.3.5 Analysis Visit for Efficacy Analyses

The use of efficacy data collected in the study will be maximized by including the assessments that are performed outside the planned visit window. Each Analysis Visit (POD 4, 8 and 15) will use an analysis window to determine the efficacy data that will be used to derive the efficacy endpoints. The actual Study Day ([Section 6.3.4](#)) will be used to define the analysis window. The analysis window for each Analysis Visit is shown in Table 3.

Table 3: Analysis Windows for Efficacy Analysis

Analysis Visit	POD4	POD8	POD15
Study Days in Analysis Window	2 – 6	7 – 11	12 – 17 or Scheduled Visit*

* Only for subjects who (i) complete at least 14 days of dosing, (ii) do not use rescue medication and (iii) have a scheduled POD15 visit after Study Day 17

If the efficacy assessments are performed at unscheduled visits occurring after Visit 2/POD1 and before Visit 5/POD15, the date of the unscheduled visits will also be used to determine the appropriate analysis window.

The efficacy assessments performed after two days following the last dose of study drug will not be used when the subjects have administered less than 14 days of study drug.

When multiple efficacy assessments fall within the same analysis window for an Analysis Visit (see [Table 3](#)), the following rules will be applied:

- If two scheduled assessments fall within the same analysis window for an Analysis Visit and one of the Analysis Visits (either before or after the Analysis Visit with two scheduled assessments) has no scheduled assessment, then the scheduled assessment data will be used for the Analysis Visit without an assessment. For example, when a subject has a scheduled POD4 visit at Study Day 3 and a scheduled POD8 visit at Study Day 6, the Analysis Visit POD4 would have two scheduled assessments and the Analysis Visit POD8 would have no data. In this case, the scheduled POD8 visit assessments will be used for the Analysis Visit POD 8.
- If one scheduled assessment and at least one unscheduled assessment fall within the same analysis window for an Analysis Visit, the latest value in the analysis window will be used for all relevant efficacy analyses.

The definition of the Analysis Visit for the efficacy analyses will be re-examined prior to database lock. If there is a need to adjust the analysis window in Table 3, the SAP will be amended to document the changes.

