6.4.2 Rescued Subjects

Any subject not responding to the study drug because of lack of efficacy at any time after randomization at Visit 2/POD1 may be rescued and placed on an appropriate alternative therapy determined by the Investigator.

The efficacy assessments performed after starting rescue medication will be excluded from the efficacy analyses.

For the primary efficacy endpoints, subjects who are rescued at any time after the first dose of study drug and before the efficacy assessments at POD15 will be considered as treatment failures (Non-responders). The same approach will be applied to derive the secondary endpoint of sustained ACF grade =0.

For both categorical and continuous secondary efficacy endpoints of ACC grade, ocular pain grade and ACF grade, the last observation carried forward (LOCF) approach will be used to impute the data for each Analysis Visit after starting rescue medication.

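### LOCF ignores the reason for leaving, so an unrescued lack-of-efficacy exit can, by two narrow routes, be an imputed responder on a primary endpoint

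*SAP*

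**What the plan says.** **Unrescued exits.** SAP 6.4.3.1: "For subjects who prematurely discontinue the study without taking rescue medication, the LOCF approach will be used to impute the missing data". Protocol 10.3.2 agrees: "For subjects who discontinue from the study prior to Visit 5 (POD15), the last observation carried forward (LOCF) approach will be used". Neither rule depends on the reason, and SAP 6.4.4 sends COVID-19 exits through the same rule. The value carried is the last one after the first dose and no later than two days after the last dose. There is one exception: "If no data can be carried forward (i.e., missing assessments at POD 4 visit or no available post-baseline assessments"), the subject is a non-responder on the categorical endpoints.

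**Rescued subjects.** For the primary endpoints, SAP 6.4.2 says that subjects "rescued at any time after the first dose of study drug and before the efficacy assessments at POD15 will be considered as treatment failures". This applies to both primaries, whatever grades were observed.

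**How a subject can leave without rescue.** Protocol 9.4.1 lists grounds for rescue, including inflammation or pain that worsens or does not improve, but adds: "Initiation of rescue medication is at the discretion of the Investigator". Protocol 6.3 states: "If a subject requests to discontinue the study drug, the subject will be withdrawn from the study as an Early Termination". It also states: "The reason for early termination/withdrawal of a subject should be recorded in the source documents and entered in the eCRF".

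**Late exit exams.** When a subject has had less than 14 days of study drug, SAP 6.3.5 says that "efficacy assessments performed after two days following the last dose of study drug will not be used". Protocol 6.2.8 lets the early termination exam take place after the termination itself.

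**The concern.** The plan treats the need for other therapy as failure on both primary endpoints, but only when that need is recorded as rescue. A subject who leaves because inflammation or pain is not controlled, with no rescue recorded before the POD15 assessments, comes under LOCF instead. If the observed and carried values at all required visits are grade 0 on one endpoint, that subject is counted on it as a responder with imputed data. Two subjects with much the same clinical course can then be scored differently according to how the exit was handled. At stake are a few entries in the primary responder counts and a foreseeable question about them.

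**Working it through.** **1. When LOCF gives a responder.** The cell endpoint needs grade 0 at POD8 and POD15. The pain endpoint needs grade 0 at POD4, POD8 and POD15. A carried value above 0 fails its endpoint, so only two routes remain. Both require that no rescue is recorded before the POD15 assessments.

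- *Route 1, the endpoint that did not drive the exit.* At Visit 4 (POD8) the cell count is 0 and pain is grade 2, and the subject asks to stop. Pain fails. The cell count of 0 is carried to POD15, so the subject is an imputed cell responder. A rescued counterpart fails both.
- *Route 2, the endpoint that worsened.* Pain is grade 0 on POD4 and then returns. The last dose is on POD6 and the exit exam on POD9. With the first dose on POD1, POD9 is Study Day 9, inside the POD8 analysis window (days 7 to 11). But 9 − 6 = 3 days, which exceeds two, so the exam is not used. The POD4 grade 0 is carried to POD8 and POD15, giving an imputed pain responder. A missed exit exam has the same effect. Rescue recorded at the POD9 visit would make this subject a failure on both primaries.

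**2. Reproducing the planning figures.** Inputs from Protocol 10.4 and SAP 4: cell responders 26% vs 12%, pain responders 57% vs 38%, two-sided 5%, 175 per arm, 5% dropout. For the pooled-variance two-proportion test without continuity correction, with p̄ the mean of the two rates,

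power = Φ{[|p1 − p2|√n − 1.96√(2p̄(1 − p̄))] / √(p1(1 − p1) + p2(1 − p2))}.

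At n = 175 this gives 91.9% for cells (stated 92%) and 94.8% for pain (stated 95%). Exactly 92% for cells needs 176 per arm (stated 175). 175/0.95 = 184.2, rounded up to 185. The plan's figures reproduce.

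**3. How many subjects.** Dropouts for all reasons at the planning rate: 0.05 × 185 = 9.25, about 9 per arm. The documents do not say how many would leave for lack of efficacy, or in which arm. As an illustration only, assume dropouts hold grade 0 at the planned responder rates. Imputed responders across all exit reasons are then:

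- Cells: 9 × 0.26 = 2.3 on APP13007 and 9 × 0.12 = 1.1 on placebo.
- Pain: 9 × 0.57 = 5.1 on APP13007 and 9 × 0.38 = 3.4 on placebo.

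**4. Effect on the tests.** Planned counts are 185 times each rate, rounded down. Test: z = (a − b)/185 ÷ √(p̄(1 − p̄) × 2/185), with p̄ = (a + b)/370. This is the Pearson chi-square without correction.

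| Scenario | Cells, APP13007 vs placebo | Pain, APP13007 vs placebo |
|---|---|---|
| As planned | 48 vs 22, 14.1 points, p = 0.0006 | 105 vs 70, 18.9 points, p = 0.0003 |
| Illustration moved to failure | 46 vs 21, 13.5 points, p = 0.0007 | 100 vs 67, 17.8 points, p = 0.0006 |
| 9 moved, APP13007 only | 39 vs 22, 9.2 points, p = 0.017 | 96 vs 70, 14.1 points, p = 0.007 |
| 9 moved, placebo only | 48 vs 13, 18.9 points, p < 0.0001 | 105 vs 61, 23.8 points, p < 0.0001 |

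Significance is lost at 35 vs 22 for cells (p = 0.061) and 88 vs 70 for pain (p = 0.059). That means moving 48 − 35 = 13 or 105 − 88 = 17 responders in the APP13007 arm alone.

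**5. Power if every planned dropout failed.** Multiplying each rate by 0.95 gives 24.7% vs 11.4% for cells and 54.2% vs 36.1% for pain. Power at 185 per arm is then 91.7% and 94.0%, against 93.3% and 95.8% with no loss. The narrower change proposed here would cost less, and the sample size can stay as it is.

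**The case against.** The case for leaving the rule alone has weight.

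- *Route 1 is a choice, not an error.* The cell count of 0 was observed, and the pain endpoint correctly fails. Whether a pain-driven exit should also fail the cell endpoint is a question of estimand. This stands, but the plan has already answered it for rescued subjects by failing both.
- *Route 2 needs several things at once:* relapse after a grade 0 exam, stopping the drug, no usable exam within two days (unscheduled visits count), and leaving with no rescue recorded. This stands and is why the number is probably small.
- *Existing cover is substantial.* The Observed-Case analysis (SAP 10.1.3, item 3) counts missing data as failure whatever the reason. SAP 10.1.4 also fails missing assessments, although it does not fail rescued subjects. SAP 10.1.2 shows imputed responders in their own row, and SAP 7.1 tabulates withdrawal reasons by arm. But none of these changes the primary analysis. The tipping point analysis does not help, because it moves only placebo non-responders to responders.

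Three stronger readings are tempting, and the documents do not support them. First, a reader might infer that anyone leaving for lack of efficacy counts as a responder; a failing last usable value is carried as a failure. Second, a reader might infer a bias towards APP13007. With equal true rates, 9 extra imputed cell responders on APP13007 alone would raise the chance of a false win from 2.5% to 26.4%, but nothing in the documents suggests that imbalance. If such exits fall mainly on placebo, LOCF works against APP13007. Third, 9 per arm might be read as a maximum. It is a planning estimate, and SAP 10.1.3, item 5, provides for more than 5% missing.

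**Conclusion.** The gap is real, narrow and minor. As written, the primary analysis can score an unrescued lack-of-efficacy exit as a responder on one endpoint or, less often, on the endpoint that worsened. The size in this trial cannot be derived from the documents, and the direction is open. At the planned effect, neither primary conclusion would change even if 9 APP13007 responders and no placebo responders were moved. That result rests on the planning rates and the 5% dropout estimate; with a smaller true effect or more dropouts the margin would shrink. The reason to act is consistency with the plan's own rescue rule, not a demonstrated threat to the result.

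**What to change.** In both SAP 6.4.3.1 and Protocol 10.3.2, state that a subject who discontinues before the POD15 assessments because of lack of efficacy, or because treatment for study-eye inflammation or pain was needed, is a non-responder on both primary endpoints and on sustained flare grade 0. Keep LOCF for other reasons.

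Classify these subjects while masked and before database lock, from the recorded reason together with the exit-visit findings. Include exit exams made more than two days after the last dose, for this classification. An exit recorded only as the subject's request, but with documented worsening pain or inflammation, is then also a non-responder.

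Cost: one matching sentence in each document, plus the classification step. The withdrawal reason already goes into the eCRF, although its categories are not shown, so a few reasons will need a masked query. A few subjects in either arm may move from imputed responder to non-responder.

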6.4.3.2 Imputation of Partial Dates for Birthday, AEs, and Medications

The day of birth date will not be collected in order to protect subjects' privacy. To calculate the age from birth date, the day will be assigned as the 1st day of the birth month.

For analysis of AEs and medications (other than the study drug), a complete date should be established in order to determine treatment emergent AEs (TEAEs) or concomitant medications. The imputation rule of partial dates will be applied for missing components of partially-reported start and stop dates for AEs and for medication use.

Partial start dates of AE and medication will be imputed as follow:

- If only the month and year are reported and the month and year of the start date is not the same as the month and year of the date of first dose of study drug, then use the first day of the month.

- If only the month and year are reported and the month and year of start date is the same as the month and year of the date of the first dose of study drug, then use the date of first dose.
- If only the year is reported, and the year of the start date is not the same as the year of first dose of study drug, then use the January 1st as the start day and month.
- If only the year is reported, and the year of the start date is the same as the year of first dose of study drug, then use the date of first dose.
- If the start date is completely unknown and the stop date is partially known or not prior to the date of first dose of study drug, then use the date of first dose.
- If the imputed start date is after the known stop date, set the start date to be the same as the stop date.

Partial stop dates of AE and medication will be imputed as follow:

- If only the month and year are reported, then use the last day of the month
- If only the year is reported, then use December 31st of that year

If the unknown dates cannot be used to determine whether an AE is treatment emergent or a medication is concomitant, the AE will be considered as treatment emergent or the medication will be considered as concomitant.

In subject data listings, birthday, start and stop date of AEs or medications (other than study drug) will be displayed as reported (i.e., no imputed values will be displayed in data listings).

6.4.4 Handling of Dropouts Due to the COVID-19 Pandemic

The [protocol Appendix A](#) describes the Early Termination/Withdrawal procedures that may be implemented because of the COVID-19 pandemic. Subjects who discontinue the study due to COVID-19 will follow the imputation rules described in [Section 6.4.3.1](#) to impute the missing efficacy data.

6.4.5 Multicenter Studies

The randomization will be stratified by study site. No study sites will be pooled for analysis purposes, as the efficacy analyses will not be adjusted for study site differences. If there is a potential site issue identified, an exploratory analysis may be performed to adjust for 'study site' in the analysis of primary efficacy endpoints.

6.4.6 Multiple Comparisons/Multiplicity

Since the comparisons of the primary efficacy endpoints will be performed in the pre-specified sequential order, the fixed-sequence hierarchical testing approach will be used to adjust for multiple comparisons. These endpoints will be tested in the sequence with the rule that once a

p-value exceeds 0.05, the endpoint further down in the sequence will not be claimed for statistical significance.

